Each participant is expected to take 1-2 hours, including paperwork, sensor application, and a maximum of 60 minutes of data collection. Each participant will be connected to a commonly used End Tidal Carbon Dioxide monitor (GE Datex-Ohmeda) and the Gabi SmartCare Gabi Band. The end tidal carbon dioxide (EtCO₂) monitor will determine performance of respiratory rate metrics (GE Healthcare S5 Compact Monitor with M-COVX (K001814) or E-CaiO (K051092) modules). Each participant will be instrumented with neonatal or pediatric nasal cannula that allows for measurement of the EtCO₂. SpO₂ sensors may be placed on the feet and/or toes for safety monitoring purposes.

Data will be simultaneously and continuously recorded from the Reference EtCO₂ monitor and the Device Under Test (DUT). Periods of quiet will be encouraged. Data will be marked for stable quiet periods that are useable for analysis. There is no additional follow-up required for the investigation.

One minute epochs will be generated from the stable data periods for analysis. For verification, the Reference EtCO₂ waveform will be scored by counting the respiratory peaks per minute (See Appendix B: Sample Waveform

Clinimark [name]	TITLE: Respiratory Rate Verification Study – Gabi SmartCare Gabi Band Study ID# PR 2022-495 Principal Investigator: [name] Site ID # 001	DOCUMENT NUMBER PR# 2022-495 SHEET 4 of 28	REV 1
---	--	---	-----------------

Scoring Form for an example). The reviewers counting the raw EtCO₂ waveform will be blinded to the results from the test device. The DUT data will be averaged over the corresponding one minute period. The Accuracy root-mean-square (A_{rms}) will be the basis for evaluation and acceptance.

To 'Pass' this test the Gabi SmartCare Gabi Band (Device Under Test) must demonstrate an Accuracy root-mean-square (A_{rms}) of ≤3.0 breaths per minute when compared to the Reference EtCO₂ monitor.

Study Population

The study population will include a minimum of 23 neonates, infants, and pediatrics from 0-12 years of age. A maximum of 60 participants will be enrolled. The participant selection will be an equitable distribution of males and females of any race with varying skin tones. An attempt will be made to include 3 darkly pigmented participants (Fitzpatrick 5 or 6) or 15% of the participant pool (whichever is larger).

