Clinimark [name]	TITLE: Respiratory Rate Verification Study – Gabi SmartCare Gabi Band Study ID# PR 2022-495 Principal Investigator: [name] Site ID # 001	DOCUMENT NUMBER PR# 2022-495 SHEET 11 of 28	REV 1
---	---	--	-----------------

Each participant will be connected to a commonly used End Tidal Carbon Dioxide monitor (GE Datex-Ohmeda) and the Gabi SmartCare Gabi Band. The end tidal carbon dioxide (EtCO₂) monitor will determine performance of respiratory rate metrics (GE Healthcare S5 Compact Monitor with M-COVX (K001814) or E-CaiO (K051092) modules). Each participant will be instrumented with neonatal or pediatric nasal cannula that allows for measurement of the EtCO₂. SpO₂ sensors may be placed on the feet and/or toes for safety monitoring purposes.

Data will be simultaneously and continuously recorded from the Reference EtCO₂ monitor and the Device Under Test (DUT). Periods of quiet will be encouraged. Data will be marked for stable quiet periods that are useable for analysis. There is no additional follow-up required for the investigation.

One minute epochs will be generated from the stable data periods for analysis. For verification, the Reference EtCO₂ waveform will be scored by counting the respiratory peaks per minute (See Appendix B: Sample Waveform Scoring Form for an example). The reviewers counting the raw EtCO₂ waveform will be blinded to the results from the test device. The DUT data will be averaged over the corresponding one minute period. The Accuracy root-mean-square (A_{rms}) will be the basis for evaluation and acceptance.

To 'Pass' this test the Gabi SmartCare Gabi Band (Device Under Test) must demonstrate a respiratory rate Accuracy root-mean-square (A_{rms}) of ≤3.0 breaths per minute when compared to the Reference EtCO₂ monitor.

Video and/or Photos

In this study photographs or video may be taken of the sensor application sites during sensor application for data collection purposes and the Study Sponsor's internal research and development purposes only. This allows the sponsor to analyze the data and observe sensor placement. Pictures may be taken of any site where we have placed equipment. The study equipment will be photographed, however, in some circumstances it may be unavoidable to not photograph the participant's face. In order to protect the participant's identity, the name will be kept confidential at all times.

Equipment

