The endpoint of interest is accuracy as measured by the Accuracy root-mean-square (A_{rms}) difference between the Device Under Test (DUT) and the Reference Respiratory Rate as counted by EtCO₂ scored waveform (Ref) for all stable respiratory periods where

Clinimark [name]	TITLE: Respiratory Rate Verification Study – Gabi SmartCare Gabi Band Study ID# PR 2022-495 Principal Investigator: [name] Site ID # 001	DOCUMENT NUMBER PR# 2022-495 SHEET 15 of 28	REV 1
--	--	---	----------

$$A_{rms} = \sqrt{\frac{\sum(DUT - Ref)^2}{n}}$$

Mean bias will also be generated:

$$Bias = \frac{1}{n} \sum_{i=1}^n (DUT_i - Ref_i)$$

Acceptance Criteria: Passing requires an A_{rms} of ≤ 3.0 cpm.

Sample Size Justification

This study will utilize a sample size of 20 participants with 7 to 11 usable data points per participant, providing ≥ 200 data points over the specified breath per minute range.

Success for this study is defined as $A_{rms} \leq 3$ cpm. The A_{rms} statistic measures accuracy of a device under test (DUT) when compared to a reference device (REF) over a range of values. Accuracy, measured by the A_{rms} statistic, can be affected by both random and systematic components of error. Here we estimate power to obtain an $A_{rms} \leq 3$ cpm for this study through simulation using parameters estimated from two preliminary studies conducted previously by Clinimark. Respiratory rate study 1 composed of 894 data points from 18 study participants. respiratory rate study 2 composed of 913 data points from 20 study participants. Both studies had respiratory rate targets of 5, 10, 15, 20, 25, 30, 35, 40 and 45 breaths per minute. The A_{rms} statistics are 2.8 cpm and 1.2 cpm for Study 1 and Study 2 respectively. For more information about the results and standard respiratory rate metrics please refer to 'Summary of Respiratory Rate Data and Results from Clinimark Studies' dated May 1, 2019. These preliminary data contain the features of real data, such as within participant correlation that is present due to repeated measurements on the same study participants. Note this sample size was conducted on studies with adult populations where paced breathing can be used to get a range of repository rates. Participants in this study will breathe at their natural rate.

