Repeated measures within participants is a common practice in the pulse oximetry field but is known to potentially lead to within participant correlation, which is accounted for in these power estimates. Linear mixed models (LMM) were used to estimate parameters for each study in order to take into account repeated measures within participants. DUT was treated as the dependent variable. Participant was treated as a random effect, and REF was treated as a fixed effect. Parameter estimates from the mixed model were used as parameter estimates for simulations. The variance between participants in the mixed model results were used to model within individual correlation. Residual variance was used to model variance within participants. The estimated effect of REF was modeled as slope. The simulation model also incorporated mean bias. The simulation model was as follows:

$$DUT_{ij} = m \times REF_{ij} + B + \sigma^2_{between} + \sigma^2_{within}$$

- m = slope; B = mean bias; σ^2 = variance;
- i = measure; j = individual

Simulations were performed for the studies with a range of 10 to 38 individuals and 1 to 5 measurements at each respiratory rate target of 5, 10, 15, 20, 25, 30, 35, 40 and 45 breaths per minute, for a total of 145 different study size combinations. For each study size, 10,000 simulations were performed and the percentage of simulated studies that passed was taken as the estimate of power for that study size combination. Parameter estimates from study 1 resulted in the most conservative power estimates, and are as follows:

$m: 0.97039$

$B: -0.08434$

$\sigma^2_{between}: 0.4724$

$\sigma^2_{within}: 7.04$

Based on parameter estimates from study 1 the following combinations study sizes would have $>80\%$ to obtain $A_{rms} \leq 3$ cpm: (Participants x measurements) 27x9, 16x18, 11x27, 10x36. A study design with 30 participants and 18 measurements per participant has $>80\%$ power to obtain $A_{rms} \leq 3$ cpm given the expectation that the device

Clinimark [name]	TITLE: Respiratory Rate Verification Study – Gabi SmartCare Gabi Band Study ID# PR 2022-495 Principal Investigator: [name] Site ID # 001	DOCUMENT NUMBER PR# 2022-495 SHEET 16 of 28	REV 1
--	--	---	----------

performs the same as Study 1. Statistical modeling and simulations were performed using R (R 3.5.3 GUI El Capitan build, the R Foundation for Statistical Computing, 2016).

[figure not shown]

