## 1 Evaluation method

Accuracy is stated in terms of the root-mean-square (rms) difference between measured values ( $\hat{x}_i$ ) and reference values ( $x_i$ ), as given by

$$A_{\text{rms}} = \sqrt{\frac{\sum_{i=1}^n (\hat{x}_i - x_i)^2}{n}}$$

$A_{\text{rms}}$  must be below 3 cpm (cycles per minute) to meet the specification.

From a statistical perspective, this specification is achieved ("success") if the **one-sided 95% confidence interval** of  $A_{\text{rms}}$  lies below 3 cpm.

In case of repeated measures per subject, the above formula is modified as follows

$$A_{rms} = \sqrt{\frac{\sum_{i=1}^n \sum_{j=1}^m (\hat{x}_{ij} - x_{ij})^2}{nm}}$$

where  $i = 1, \dots, n$  indexes the subjects, and  $j = 1, \dots, m$  indexes the repeated measures within a subject.

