**This document provides information on the sample size requirement for such a study.**

## 2 Paragraph for the study protocol

### 4 paired readings per subject

Assuming that the mean of the absolute differences between measured values and reference values is  $\leq 2$  and that the between-subject and within-subject variances are  $\leq 0.75$ , a minimum sample size of 12 patients (resulting in 48 paired data points) was computed to achieve  $\geq 80\%$  power in demonstrating that  $A_{rms}$  is below 3 cpm, at the 95% confidence level.

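### The Protocol passes the device on the observed A_rms while the SAP requires a one-sided 95% confidence limit below 3 cpm; no available text says which rule governs, and each power claim uses its own rule and variances

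*Protocol*

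**What the plan says.** **Protocol.** The pass rule appears three times, each time as a condition on A_rms itself. In the Summary (Protocol Overview) the device "must demonstrate an Accuracy root-mean-square (A_{rms}) of ≤3.0 breaths per minute". Under Method it "must demonstrate a respiratory rate Accuracy root-mean-square (A_{rms}) of ≤3.0 breaths per minute". Under Endpoint / Comparator: "Acceptance Criteria: Passing requires an A_{rms} of ≤ 3.0 cpm". The Sample Size Justification repeats the threshold as its definition of success. No confidence interval, alpha or confidence level is given. Power is defined to match: "the percentage of simulated studies that passed was taken as the estimate of power". The planned size is given as "This study will utilize a sample size of 20 participants with 7 to 11 usable data points per participant", while the design sections set a minimum of 23 participants.

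**SAP.** Section 1 (Evaluation method) takes the same 3 cpm specification and counts it as met "if the one-sided 95% confidence interval of" A_rms lies below 3. Section 2 offers sample-size text for the Protocol on that basis, for example "a minimum sample size of 12 patients (resulting in 48 paired data points) was computed to achieve" at least 80% power at the 95% confidence level. The Protocol's sample-size section contains none of that text.

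**Inputs.** The Protocol simulates with slope 0.97039, bias −0.08434, between-participant variance 0.4724 and within-participant variance 7.04, explaining that "Parameter estimates from study 1 resulted in the most conservative power estimates". The SAP assumes a bias of up to 2 and both variances at 0.75. The largest population A_rms in its scenario table is 2.45.

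**The concern.** This is the primary pass/fail decision. An observed A_rms a little below 3 satisfies the Protocol and can fail the SAP. If nothing fixes the rule beforehand, it can be chosen once the result is known.

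The rules also support different claims. An observed value at or below 3 does not show that the true A_rms is below 3 with 95% confidence, which is the claim the SAP is sized for.

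Nor can a reader tell which power figure applies. Neither document gives power for the confidence rule at Study 1 performance, although the Protocol rests its 30 × 18 power statement on the expectation that the device performs as in Study 1.

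**Working it through.** **Models**

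- Protocol (Sample Size Justification): DUT − REF = (0.97039 − 1)·REF − 0.08434 + b + e, with Var(b) = 0.4724 and Var(e) = 7.04. REF takes the nine targets 5, 10, …, 45, or is evenly spaced over 5–45 for 7 or 11 readings.
- SAP (section 3): d = μ₀ + b + e, with μ₀ = 2 and both variances 0.75.
- Observed-value rule: pass if the study's A_rms ≤ 3.0.
- Confidence rule: pass if the 95th percentile of A_rms over 1,000 bootstrap resamples of whole participants is below 3.0.

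**Population A_rms**

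- Protocol: the mean of REF is 25 and the mean of REF² is 7125/9 = 791.67. The mean squared systematic error is 0.02961² × 791.67 + 2 × 0.02961 × 0.08434 × 25 + 0.08434² = 0.694 + 0.125 + 0.007 = 0.826. A_rms = √(0.826 + 0.4724 + 7.04) = √8.338 = 2.89. The Protocol states 2.8 for Study 1.
- SAP: √(2² + 0.75 + 0.75) = √5.5 = 2.35.

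**Reproducing the plans' own figures**

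- The Protocol's sizes under the observed-value rule give about 80–81% (27×9), 80% (16×18), 81–82% (11×27), 81–82% (10×36) and 88% (30×18). The >80% statements therefore hold to within simulation error, and only under a rule with no confidence limit.
- The SAP's sizes under the confidence rule give 84% (12×4), 86% (11×10) and 85% (10×20). The ≥80% statements hold.

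**Both rules at Study 1 parameters**

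| Participants × readings | Observed-value rule | Confidence rule |
|---|---|---|
| 20×7 | 74% | 22% |
| 20×9 | 77% | 24% |
| 20×11 | 79% | 26% |
| 23×9 | 79% | 24–25% |
| Protocol's five sizes | 80–88% | 26–37% |
| 60×9 | about 89% | about 38% |
| 60×18 | about 95% | about 52% |

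At 23×9 about 54% of studies pass the first rule and fail the second (79 − 25).

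**Sensitivity at 23×9**

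| Assumed performance | Confidence rule | Pass Protocol, fail SAP |
|---|---|---|
| Study 1 as modelled (A_rms 2.89) | 24–25% | 54% |
| Study 1 errors scaled to A_rms 2.8 | about 46% | 46–47% |
| REF centred at 25 (A_rms 2.77; does not reproduce the Protocol's sizes) | 56% | 39–40% |
| Slope dropped (A_rms 2.74; does not reproduce them either) | 63% | 34% |
| SAP bias 2, variances 1.0/1.0 | 89% | 11% |
| SAP bias 2, variances 0.75/0.75 | 98% | 2% |
| Study 2 A_rms of 1.2 (variances assumed, not given) | about 100% | 0% |

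For Study 2, two assumed splits were tried: variances 0.72/0.72 with no bias, and 0.22/0.22 with bias 1.

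**Where the rules part.** With Study 1-type error at 23×9, the confidence rule needs an observed A_rms of about 2.78 or less (roughly 2.72–2.83, depending on the sample). It reaches 80% power only if the true A_rms is about 2.65.

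**At a true A_rms of 3.0, 23×9.** The observed-value rule passes 51–53% and the confidence rule 8–11%. This was checked with Study 1 errors scaled up, and with bias 2 and variances 2.5/2.5, since √(4 + 5) = 3. The nominal rate for the confidence rule is 5%, so the percentile bootstrap is somewhat lenient and the confidence-rule figures above are, if anything, slightly high.

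**The case against.** The strongest reply is that the Protocol is consistent within itself and governs. It states the observed-value rule repeatedly, computes power for it, and bars investigators from departing from the plan. The SAP describes itself as providing sample-size information and covers children only up to 5 years, whereas most of the Protocol goes to 12, so it may reflect earlier planning. That is plausible, but it is inference. The SAP's definition of success stands under its evaluation-method heading. If the Protocol's rule governs, the SAP's sample sizes support a test that will not be run. Part of the SAP was not available, so the point about precedence is limited to the text that could be read.

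A second reply is that the size of the conflict depends on true performance. This stands. The share of studies with opposite verdicts runs from 0 to 54% across the scenarios above. Study 1 is weak evidence here: adults, paced breathing, and no statement that it tested this device. The 24–25% is therefore a scenario value and not a forecast. It does not automatically improve with other breathing rates: assumed REF ranges of 15–25, 20–40 and 25–45 give 40%, 20% and 12% under the confidence rule.

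Third, passing about half of studies at the threshold is a property of any observed-value rule, and the Protocol claims no confidence level. That is correct, and it makes keeping the rule legitimate provided no such claim is attached to a pass.

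**Conclusion.** The concern holds and should be settled before the data are analysed. One specification carries two incompatible pass rules, and the available text does not rank them. Each power claim is arithmetically sound under its own rule and inputs, so the fault is a conflict between documents and not a calculation error.

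The practical effect is large if the true A_rms is near the Protocol's Study 1 value and negligible if the device performs as the SAP assumes. These sizes rest on the two stated error models with normal errors, on REF spread over 5–45 for the Study 1 scenario, and on a percentile bootstrap by participant. The contradiction itself rests on none of them.

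**What to change.** State one governing rule in the same words in the Protocol (Protocol Overview, Method, Endpoint / Comparator and the success definition under Sample Size Justification) and in SAP section 1. Settle at the same time whether the threshold is at or below 3.0, as in the Protocol, or strictly below 3, as in the SAP.

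- **Preferred:** pass if the one-sided 95% upper confidence limit of A_rms, clustered by participant, is below 3.0, with the observed A_rms reported alongside. Name one interval method, because SAP section 3 lists several.
- **Acceptable:** keep the observed-value rule, say so in the SAP, and do not describe a pass as demonstrated at 95% confidence.

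Under either choice, restate power for that rule at the planned size (20 to 23 participants, 7 to 11 readings) with one justified set of variances, as a range that includes Study 1 and Study 2 performance.

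The work is a few wording changes and a rerun of existing simulations. The consequence may be larger: under the confidence rule at Study 1 performance, power is about 24% at the planned size. Even the 60-participant ceiling gives about 38% with 9 readings and 52% with 18. If errors are scaled to the stated A_rms of 2.8, power at 23×9 is about 46%. The sponsor would have to justify better expected performance, accept low stated power, or keep the observed-value rule and limit what a pass claims.

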Investigators Records and Reporting	25
Records 21 CFR 812.140 (a)(3)(i).....	25
Reports 21 CFR 812.150 (a) 1,2,5,7	25
Unanticipated adverse device effects.....	25
Withdrawal of IRB approval.....	25
Informed consent.....	25
Other	25
Withdrawal, Early Termination or Suspension of the Investigation	25
Publication Policy.....	26
Attachment A - Protocol Signature Page	27
Appendix B: Sample Waveform Scoring Form	28

Clinimark [name]	TITLE: Respiratory Rate Verification Study – Gabi SmartCare Gabi Band Study ID# PR 2022-495 Principal Investigator: [name] Site ID # 001	DOCUMENT NUMBER PR# 2022-495 SHEET 8 of 28	REV 1
---	--	---	-----------------

Respiratory Rate Verification Study - Gabi SmartCare Gabi Band

PR 2022-495

Objectives of the Clinical Investigation Plan

The purpose of this study is to conduct a Respiratory Rate accuracy Verification study comparing the Gabi SmartCare Gabi Band to the Reference, an FDA cleared End Tidal Carbon Dioxide monitor (GE Datex-Ohmeda).

The testing will be conducted in order to obtain a full data set for Verification on a minimum of 23 participants. Multiple developmental phases may be conducted and will be reviewed for readiness for continuation to Verification. If modifications are warranted, the initial data sets will be used for algorithm development. The full Verification set will be collected independent of developmental data sets. The study will be split up into two phases:

- Phase I with a minimum of 8 subjects
- Phase II with a minimum of 15 subjects

Identification and Description of the Investigational Device

The Gabi device consists of a sensor head with an attached armband to make the wearable device. The sensor head contains a photoplethysmography sensor (PPG) and all other electronics. The PPG sensor is seated on the underside of the sensor head to maintain skin contact. All data is stored on the collection tablet and uploaded to the Gabi Cloud for analysis when data collection is stopped.

[figure not shown]

Figure 1: The Gabi SmartCare Gabi Band – The Device Under Test

The intended purpose of the Device Under Test is continuous, non-invasive monitoring on the neonatal, infant, and pediatric populations. For this evaluation, the device will be run in a continuous data collection mode. The accompanying acquisition software will be provided by Gabi SmartCare.

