The nasal cannula are made of soft, flexible plastic so as to minimize the discomfort level as much as is reasonably possible. Materials may cause some skin irritations. Insertion and removal of a nasal cannula may cause nasal irritation, discomfort, or pain.

General Electrical Hazards

Electrical hazards are a potential risk with all electrical equipment. The equipment used in this study has been designed to meet applicable safety standards. The equipment will be safety and functionally tested prior to participant use. The possibility of any electrical hazard is extremely remote.

Benefits

The benefits to the study are to the advancement of non-invasive medical monitoring of patients by improving accuracy and performance of the monitors. There are no direct benefits to the participants involvement in this study other than being a paid volunteer. The only alternative to this study is to NOT participate.

Design of the Clinical Investigation

Method

The purpose of this study is to conduct a Respiratory Rate accuracy Verification comparing the Gabi SmartCare Gabi Band to the Reference, an FDA cleared End Tidal Carbon Dioxide monitor (GE Datex-Ohmeda).

This study is a comparative, single-center, non-randomized study in a minimum of 23 participants for the verification. Each participant test is expected to take approximately 1-2 hours. Typically, up to 4 participants will be run per day. It is expected that the data collection will take two days for Phase II and four days for Phase II. A maximum of 60 participants will be enrolled. An attempt will be made to include 3 darkly pigmented participants (Fitzpatrick of 5 or 6) or 15% of the participant pool (whichever is larger). Participants will be from 0-12 years of age with the following distribution:

Population	Age Population	Requirement
Neonates	0-28 Days	No requirement
Infant	>1 month – 24 months	Minimum 30% of participants
Pediatrics	>2 years – 12 years	Minimum 30% of participants

The parent or guardian will be provided an IRB approved Informed Consent. As applicable, parent or guardian will be told about any new information that might change their decision to participate. Participants whose parent or guardian have completed the informed consent, completed the Participant Demographics and Screening Record Form, and met inclusion criteria and none of the exclusion criteria will be enrolled in the study. Participants ranging in age 7-12 years will additionally go through an Assent process.

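### The planned 20 participants with 7 to 11 points each yield 140 to 220 data points, so 200 is not assured; the 20 conflicts with a minimum of 23 elsewhere, and the closing power sentence is for a different design

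*Protocol*

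**What the plan says.** The Sample Size Justification opens with "This study will utilize a sample size of 20 participants with 7 to 11 usable data points per participant, providing ≥ 200 data points", and the sentence goes on "over the specified breath per minute range". The same section says that "Participants in this study will breathe at their natural rate".

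Elsewhere the size is 23. The Method section describes a study "in a minimum of 23 participants for the verification". The Summary, the Objectives and the Study Population section also give a minimum of 23, with a maximum enrolment of 60. The 23 is the sum of the two phase minimums, 8 for Phase I and 15 for Phase II ("Phase II with a minimum of 15 subjects"). The Objectives section says that initial data sets go to algorithm development if modifications are warranted, and that "The full Verification set will be collected independent of developmental data sets".

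On power, the section reports simulations based on two adult studies with paced breathing, whose A_rms values were "2.8 cpm and 1.2 cpm for Study 1 and Study 2 respectively". It says that "Parameter estimates from study 1 resulted in the most conservative power estimates". It then lists four combinations (participants x measurements) with more than 80% power: 27x9, 16x18, 11x27 and 10x36. It closes by giving more than 80% for 30x18. The text states no power for 20 or 23 participants.

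**The concern.** A sample size section should say how many participants and readings are planned and what chance of passing they give. Here the stated yield does not follow from the stated inputs. The number of participants differs from the rest of the protocol, and the closing power statement belongs to a study of 540 readings. A reader cannot tell which verification set the calculation supports, and could take the figure of more than 80% to cover a design about a third of that size or smaller. What is at stake is the chance of passing and the clarity of the plan. None of this biases the A_rms estimate.

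**Working it through.** **Yield** (all inputs from the protocol)

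| Participants | Points each | Total | Mean needed for 200 |
|---|---|---|---|
| 20 | 7 to 11 | 20 x 7 = 140 to 20 x 11 = 220 | 200 / 20 = 10.0 |
| 23 | 7 to 11 | 23 x 7 = 161 to 23 x 11 = 253 | 200 / 23 = 8.7 |
| 30 | 18 | 30 x 18 = 540 | not applicable |

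A yield of 200 lies inside both planned ranges, but neither size guarantees it.

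**Model.** The Study 1 parameters are slope m = 0.97039, B = -0.08434, between-participant variance 0.4724 and within-participant variance 7.04. The reference rates are the nine targets 5, 10, ..., 45 per minute. I read the two variance terms in the printed equation as normal random effects and B as an intercept:

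d = (m - 1) x REF + B + b + e, with b ~ N(0, 0.4724) per participant and e ~ N(0, 7.04) per reading.

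A simulated study passes if its pooled A_rms is 3.0 or less.

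**Model A_rms.** The mean of ((m - 1) x REF + B)^2 over the nine targets is 0.826. So A_rms = sqrt(0.826 + 0.4724 + 7.04) = 2.89.

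**Reproducing the protocol's figures** (40,000 simulated studies per size, Monte Carlo standard error about 0.2 percentage points):

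| Design | Protocol | Recomputed |
|---|---|---|
| 27x9 | >80% | 80.2% |
| 16x18 | >80% | 80.9% |
| 11x27 | >80% | 80.6% |
| 10x36 | >80% | 81.8% |
| 30x18 | >80% | 87.7% |

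All five statements hold.

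**Planned sizes on the protocol's grid.** The grid is 10 to 38 participants (29 sizes) by 1 to 5 measurements at each of nine targets. That gives 29 x 5 = 145 combinations, the number the protocol reports. So 20x9 and 23x9 are grid cells, while 7, 8, 10 and 11 points are not.

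- 20x9: 77.4%; a second run of 100,000 studies gave 77.1%.
- 23x9: 78.6%; the second run gave 78.5%.

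**Sensitivity at 9 points per participant**

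| Assumption | 20x9 | 23x9 |
|---|---|---|
| As above (model A_rms 2.89) | about 77% | about 78.5% |
| Residual variance lowered to 6.54, so that model A_rms is 2.80 | 90.6% | 92.2% |
| B read as the bias at mid-range, 25/min (model A_rms 2.77) | 94.3% | 95.4% |
| Natural rates, participant means 15 to 30/min | 84.3% | 86.2% |
| Natural rates, participant means 20 to 30/min | 81.4% | 82.7% |
| Natural rates, participant means 25 to 40/min | 65.6% | 67.5% |
| Natural rates, participant means 20 to 45/min | 65.2% | 66.2% |

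The natural-rate rows are my assumptions, since the documents give no distribution: participant means are uniform over the interval and the within-participant SD is 2. Over 7 to 11 points, the two higher-rate cases give about 64 to 68%. Power falls at higher rates because, with a slope below 1, the model's negative bias grows with rate.

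**The case against.** **The figure of 200 is reachable.** It lies inside 140 to 220, and the maximum of 60 leaves room to recruit. This stands. A reader might infer that the design cannot give 200 points, which would be wrong; the defect is that the sentence states as a result something its inputs only allow.

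**The power may already be shown.** Both 20x9 and 23x9 were on the simulated grid, and Figure 3 is captioned as plotting power by participants and measurements. The figure probably contains these values but is not available in this copy. So the finding is limited to the text, and it would be unfair to say that the power was never computed.

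**The SAP gives adequate sizes.** SAP section 2 reports at least 80% power for 12x4, 11x10 and 10x20, and its grid includes 20x10. But those results assume variances of at most 0.75, against 0.4724 and 7.04 in the protocol, and use a one-sided 95% confidence limit instead of a point estimate. They do not supply the power of the protocol's design under the protocol's parameters.

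**The recomputed power is fragile.** This stands, in both directions. The protocol calls B a mean bias. Read as the bias at mid-range, it gives a model A_rms of 2.77, nearer Study 1's reported 2.8 than 2.89 is. That reading, however, gives 96 to 98% at the four listed sizes, so the intercept reading is probably what was run. If the children's rates lie mostly in the upper range, power is lower.

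**Twenty may mean evaluable out of 23 enrolled.** No passage says so or gives an attrition allowance. The Duration section's 5 to 7 days at typically four participants a day implies 20 to 28, which fits either number.

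**Phase I may not count.** A reader might infer that only the 15 Phase II participants would be analysed. The documents do not support that as the planned design: developmental use of early data is conditional, the Method section sets the minimum of 23 for verification itself, and enrolment may rise to 60. What remains is that the protocol should say whether Phase I counts.

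**Conclusion.** The concern holds in a limited form. The stated yield of at least 200 is not assured: it is 140 to 220 at 20 participants and 161 to 253 at 23. The planned size is inconsistent within the protocol, and the closing power sentence describes a design that is not planned.

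With Study 1 parameters, B as intercept, rates spread evenly over 5 to 45/min and the point-estimate rule, power is about 77% at 20x9 and 78.5% at 23x9. That is roughly 1.5 to 3 points under the 80% level used to list adequate sizes. A reader might conclude that the study is underpowered. The documents do not establish that, because plausible readings of the same inputs move the figure from about 65% to about 95%. The firm conclusion is that the text does not tie the planned size to a stated power.

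**What to change.** - Use one size throughout and give its true yield: 20 participants, 140 to 220 points; or a minimum of 23, 161 to 253 points. If 200 is a requirement and not a forecast, state it as a separate minimum.
- State the power of the chosen size from the existing grid (about 77% for 20x9, about 78.5% for 23x9). Label it as resting on Study 1 parameters, adult paced rates of 5 to 45/min and the point-estimate rule A_rms of 3.0 or less. If power at 7, 8, 10 or 11 points is to be quoted, rerun the code for those numbers.
- Label 30x18 as an example and not the planned design.
- State whether Phase I participants count towards the 23.
- Define or remove the reference to a specified range of breathing rates.

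The cost is protocol wording and, at most, a rerun of existing code. The stated yield and power become slightly less favourable. No participants are added.
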